**Notes:**

- The following information will be recorded for each patient at each clinic visit for both treatment arms, using a standardized data collection form: Date of follow up; pain (0/10); episodes of bleeding (# and whether mild, moderate, or severe); amount of crust (mild, moderate, or severe); amount of fibrin (mild, moderate, or severe); size

**Study Title: Prospective randomized clinical trial comparing outcomes of secondary intention wound care methods**

of wound (width, length, and depth); whether the wound is completely healed (completely re-epithelialized); any tumor recurrence (as determined by physician); if excess granulation tissue is present (as determined by being higher than the level of the surrounding skin); if there is infection (as determined by the physician); whether culture was taken; and degree of debridement (none, mild, moderate, or severe).

- At each visit, we will review the treatment method with the patient (i.e. whether aggressive or minimal debridement), reinforce the instructions, and give them another written copy of their wound care methods)
- We will measure time to 50% healing of the wound for all patients.
- *Both intervention arms (aggressive debridement and minimal debridement) are accepted methods of post-operative care for secondary intention wounds. While both methods are practiced at Lahey Clinic, there is no known, published “standard-of-care” in the literature for such wounds. This is because there have been no randomized controlled trials undertaken comparing efficacy of these two methods. That is the purpose of this study.*
- *It is the standard of care to have patients with wounds healing by secondary intention return to clinic for wound checks until the wounds is sufficiently healed; however, the exact interval period is up to the discretion of the provider. In this study, we will be following up weekly with patients receiving frequent debridement and biweekly with patients receiving minimal debridement. All patients will continue to be followed until their wounds are healed.*

Ongoing Care: The patient will return to clinic for evaluation until defect is completely healed, as determined by the principal investigator.

The follow-up intervals are as noted above.

- Patients will be asked to record the date on which their wound healed, and this will be reviewed over the phone or at their next clinic appointment.
- Once the wound is determined to be completely healed (full re-epithelialization), the patient will be asked to complete the Patient Scar Assessment Questionnaire. The Patient Scar Assessment Questionnaire is a validated questionnaire used standardly in Dermatology for assessing patient-based outcome measures of scarring. It consists of 5 subscales: appearance, symptoms, consciousness, satisfaction with appearance and satisfaction with symptoms. Each subscale consists of a set of items with 4-point categorical responses, scoring 1 to 4 points (with 1 point assigned to the most favorable category and 4 assigned to the least favorable). It has been demonstrated to be a reliable and valid measure of patients' perception of scarring.

**Study Title: Prospective randomized clinical trial comparing outcomes of secondary intention wound care methods**

- Photographs of healed wounds will be provided to a third-party, blinded investigator, who will evaluate these photos using the validated Visual Analog Scale.
- If the patient’s wound is not healed by 16 weeks, then the patient is deemed to be a treatment failure. The patient will be withdrawn from the treatment part of the study. The wound care instructions will be changed based on the patient’s wound characteristics and medical comorbidities and they will continue to receive medical care until their wound is completely healed. We will continue to collect data on these patients until their wounds are completely healed and may describe their post-operative wound course in qualitative terms.

**Statistical Issues**

Sample Size/Power	Time to healing will be the primary outcome measure and will be compared between groups using a two-sided t-test. There is limited literature regarding similar patients to help guide estimates for a power analysis. Based on a review of the literature,  and a brief review of patients previously seen at our clinic, we powered the study to detect a difference in healing time between treatment groups of 14 days, and assumed a standard deviation (SD) of 15 days. To obtain 80% power to detect such a difference, assuming alpha=0.05 and a two-sided t-test, 20 patients per group (40 total) are required.
Anticipated Strengths	We performed a priori power analysis. We are using a randomized study design with validated survey instruments. We plan to use a blinded reviewer of the final cosmetic outcome.
Anticipated Limitations	Given the nature of our study, it will not be possible to conceal treatment arm to patients or providers, though assessment of the final outcome will be by blinded reviewer. If variability in wound healing is greater than anticipated, we may not have statistical power to detect differences between groups; however, the estimates we obtain will help inform future studies. The minimal debridement group will be seen by the clinician every two weeks; while the aggressive debridement group will be seen weekly. It is therefore possible that ascertainment of time to wound healing will differ between groups. However, we hope to avoid this bias checking with the minimal debridement group by phone on weeks where they have no scheduled visit.

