**Study Design / Procedures:**

Randomized Clinical Trial

**Enrollment** At the baseline visit, after the patient has signed consent and been randomized to their specific treatment arm, we will obtain basic demographic information including age, sex and race, as well as pertinent comorbidities that would affect wound healing such as diabetes, venous stasis, immunosuppression and tobacco use (if documented as problems in the patient's chart). Wound defect width, length, and depth will also be measured at baseline, prior to any intervention.

**Intervention Arms:** 1) Aggressive debridement: Aggressive and frequent debridement of fibrin and crust from the wound base down to pinpoint bleeding, both by the patient as part of daily wound care at home, and also by the clinician (either physician or experienced dermatologic surgery nurse) during follow-up visits. Silver nitrate will be used to treat excessive granulation tissue only if the granulation tissue is higher than the level of surrounding skin. Patients will return weekly until healed. Patients will be provided with detailed instructions and guidelines to help determine whether healing has taken place.

2) Minimal debridement: No debridement of fibrin by the patient or the clinician. Exceptions include debridement of dried crust or eschar. Silver nitrate will be used to treat excessive granulation tissue only if the granulation tissue is higher than the level of surrounding skin. Patients will return every two weeks until healed. In between visits at weekly intervals, the patient will be contacted by phone to determine if healing has occurred in between clinic visits. Patients will be provided with detailed instructions and guidelines to help determine whether healing has taken place.

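### No rule says which date counts as healing, and the arms are checked differently, so the primary comparison may be biased: by 0 to +3.5 days with one date source, −3.5 to +7 with mixed sources

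*Combined protocol and SAP*

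**What the plan says.** All references are to the combined protocol and SAP.

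- **Outcome.** Outcomes Measures names time to healing as primary but does not define the event date.
- **Clinic record.** Study Design / Procedures has the aggressive arm seen weekly. For the minimal arm it says: "Patients will return every two weeks until healed". Healing status is on the form used at clinic visits: "The following information will be recorded for each patient at each clinic visit for both treatment arms, using a standardized data collection form". Under Ongoing Care, "The patient will return to clinic for evaluation until defect is completely healed, as determined by the principal investigator"; the Study Calendar repeats this for each arm.
- **Phone record, minimal arm only.** Between visits, "the patient will be contacted by phone to determine if healing has occurred in between clinic visits".
- **Patient record, without distinction of arm.** Patients are asked to "record the date on which their wound healed, and this will be reviewed over the phone or at their next clinic appointment".
- **Stated limitation.** Statistical Issues, Anticipated Limitations, says: "It is therefore possible that ascertainment of time to wound healing will differ between groups". It adds: "we hope to avoid this bias checking with the minimal debridement group by phone on weeks where they have no scheduled visit".
- **Analysis.** The Analytic Plan specifies a t-test, replaced by a log-rank test if times are not normal or are censored. It does not choose among these records or say what to do when they disagree.

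**The concern.** A healing date found at a scheduled check is late by part of the checking interval, and the clinic interval is twice as long in the minimal arm. Part of any observed difference could then reflect the schedule and not the treatment. The calls correct this only if a call, or the date it elicits, becomes the event date. Ongoing Care and the Study Calendar point instead to the investigator's determination in clinic. On that reading the calls do not affect the endpoint.

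If the call does count, a minimal-arm date can rest on self-report while every aggressive-arm date rests on examination. With no rule, the date could be settled after the data are seen, in an open-label trial of 40 patients, and the choice can move the result in either direction. The blinded reviewer does not help here, because that person rates photographs for cosmetic outcome and does not date healing.

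**Working it through.** **Inputs.** From Sample Size/Power: difference 14 days, SD 15 days, 20 per arm, two-sided α = 0.05. From Study Design / Procedures: clinic interval 7 days (aggressive) and 14 days (minimal), with a phone check in the minimal arm's off weeks. Not in the documents, so assumed: healing uniform between checks, visits on schedule, patient dates accurate, SD 15 referring to exact healing times.

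**Step 1: the plan's own figure.** The noncentral t gives 79.9% power at 19 per arm and 82.0% at 20. The stated 20 per group is therefore reproduced.

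**Step 2: mean delay.** This is half the interval: 7/2 = 3.5 days for weekly checks, 14/2 = 7 days for two-weekly checks, and 0 for an accurate patient date.

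**Step 3: bias = minimal delay − aggressive delay.** A positive value makes minimal debridement look slower.

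| Aggressive arm dated by | Minimal arm dated by | Bias (days) |
|---|---|---|
| Patient date | Patient date | 0 − 0 = 0 |
| First weekly check | First weekly check (clinic or phone) | 3.5 − 3.5 = 0 |
| Clinic | Clinic | 7 − 3.5 = +3.5 |
| Clinic | Patient date | 0 − 3.5 = −3.5 |
| Patient date | First weekly check (clinic or phone) | 3.5 − 0 = +3.5 |
| Patient date | Clinic | 7 − 0 = +7 |

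The first three rows use one source and span 0 to +3.5. The last three mix sources and span −3.5 to +7. Simulation with normal times and assumed means of 30, 45 and 60 days gives the same values to within 0.03 days, so the unknown mean hardly matters.

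**Step 4: effect on the t-test.** A uniform delay over an interval L adds L²/12 to the variance: 49/12 = 4.08 for weekly and 196/12 = 16.33 for two-weekly checks.

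- Clinic dates in both arms: SD = √((225 + 4.08 + 225 + 16.33)/2) = 15.34. With no true difference, a 3.5-day shift gives 10.8% rejection. A true 14-day benefit of minimal debridement appears as 14 − 3.5 = 10.5 days, with power 56.0%.
- Clinic (aggressive) against patient date (minimal): SD = √((225 + 4.08 + 225)/2) = 15.07. Rejection is 11.1%. Power for a true 14-day benefit of aggressive debridement is 57.4%.
- Patient date (aggressive) against clinic (minimal): SD = √((225 + 225 + 16.33)/2) = 15.27. A 7-day shift gives about 29% rejection.

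**Step 5: how far the calls help.** Suppose the aggressive arm is dated by clinic and weekly detection works in a share s of minimal-arm patients. The bias is then 3.5(1 − s): 1.75, 0.9 and 0.35 days at s = 50%, 75% and 90%, with t-test error 6.4%, 5.5% and 5.1%.

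**Step 6: log-rank.** This test applies only if times are non-normal or censored. In a lognormal simulation (assumed mean 45, SD 15, censored at day 112), its error is about 16% with clinic dates in both arms and about 6% with patient dates in both.

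**Step 7: power under a common rule, 20 per arm, 14 days.** Patient dates, SD 15: 82.0%. First weekly detection, √(225 + 4.08) = 15.13: 81.3%. Shared even-week grid, √(225 + 16.33) = 15.53: 79.3%.

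**The case against.** The protocol discloses the problem and acts on it. The calls give both arms a weekly check, and the patient-recorded date is requested in both arms, so a common source exists. Nothing says that the arms will be dated from different sources. If the calls work in 75% to 90% of minimal-arm patients, the remaining bias is under a day. A call may also simply be the occasion on which the patient's date is reviewed, so the records need not be three separate dates. And since visits continue until the investigator finds the wound healed, a phone report alone arguably does not end them.

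Much of this stands. The bias is conditional, the mixed-source rows are possibilities that the text leaves open and not its stated intention, and a confirming visit is already implied by the questionnaire and photographs at healing. What does not follow is that the matter is settled: the safeguards work only if they feed the event date, and no section says that they do.

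Two stronger readings are tempting. A reader might infer that the primary comparison is biased as planned. The documents do not support that, because a date collected in both arms would bring the expected schedule bias to about 0. A reader might also infer symmetric limits of 3.5 days either way. That is neither range: −3.5 already requires mixed sources, and once mixing is allowed the upper end is +7.

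**Conclusion.** The concern holds in conditional form. Ascertainment differs by arm and the event date is undefined, so the primary comparison may be biased. The expected size is 0 to +3.5 days with one date source in both arms, and −3.5 to +7 days with different sources. Reading investigator determination at clinic visits literally gives +3.5 days, which is 3.5/14 = 25% of the target difference.

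These are mean shifts under the assumptions listed above. An individual delay can reach 7 days with weekly checks or 14 with two-weekly checks. Patients' misjudgement of re-epithelialization could add bias of either sign, which cannot be sized from the documents. The sample size calculation is not in question. The plan should be corrected on this point, and the correction is small.

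**What to change.** State in the Analytic Plan one event-date rule, applied identically to both arms, with a rule for dates that disagree. Acceptable options are:

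1. The patient-recorded date in both arms, subject to investigator confirmation. This loses no power if dates are accurate, but rests on unblinded self-report.
2. The first weekly clinic-or-phone detection in both arms, subject to investigator confirmation. Power is about 81%; it relies on self-report in the minimal arm's off weeks.
3. Investigator-confirmed healing on a shared even-week grid. This does not rely on self-report, but the time scale is coarser and power is about 79% (81.3% with 21 per arm). If each visit is missed with probability p, a residual bias of 7p/(1 − p) remains: about 0.4, 0.8 and 1.75 days at assumed rates of 5%, 10% and 20%.

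Whichever is chosen, state in the procedures that a minimal-arm patient who reports healing by phone still attends the next scheduled visit for confirmation. Add a sensitivity analysis that treats healing as interval-censored between the last not-healed and first healed examination, and report missed visits by arm.

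The cost is a few sentences, slightly more analysis work, and at most one already scheduled visit per minimal-arm patient. That means about 10 of the 20 if healing is spread evenly over each fortnight, and never more than 20 visits in total.

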**Study Title: Prospective randomized clinical trial comparing outcomes of secondary intention wound care methods**

**Study Calendar / Schematic / Schedule:**

Day 1:

Eligible Dermatology patients at Lahey Clinic who have undergone Mohs surgery or excision and have postoperative defects allowed to heal by secondary intention, who satisfy the inclusion/exclusion criteria and who agree to enter the study and sign the consent form, are randomized to different intervention groups:

Aggressive Debridement Arm vs Minimal Debridement Arm.

Aggressive Debridement Arm:

Week 1-Week 16:

The patient returns to the clinic every week for evaluation until the wound is completely healed, as determined by the principal investigator.

Minimal Debridement Arm:

Week 2-Week 16:

The patient returns to the clinic every two weeks for evaluation until the wound is completely healed, as determined by the principal investigator.

**Potential Risks and Discomforts:**

The probability and magnitude of harm or discomfort anticipated in the research are not greater in and of themselves than those ordinarily encountered during routine post-operative care, including the performance of routine physical or psychological examinations or tests. However, since this study is comparing two methods of treating post-surgical wounds, it is possible that one treatment method is significantly more effective than another. By participating in this study, there is the risk that the patients randomized to the less effective treatment method may delay their wound healing. It is also possible that one group of patients may have more side effects than the other. For example, patients in the aggressive debridement group may experience more bleeding, pain, and scarring than the minimal debridement group.

**Potential Benefits:**

Improved knowledge of most effective post-operative secondary intention wound care methods.

**Statistical Analysis:**

Analytic Plan

Differences in demographic and wound characteristics between groups will be compared to evaluate balance between groups. Differences between treatments arms for the primary (time-to-healing) and continuous secondary outcomes (patient satisfaction with their scar, cosmetic appearance, number of complications) will be analyzed using t-tests for independent groups. If time-to-healing is not distributed normally, or if there are censored observations (e.g., loss to follow-up, or not all patients have healed by the 16-week endpoint), a log-rank test will be used to test for differences in

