**Subject Enrollment: / Consent Process / Screening / Randomization:**

Randomization

Block randomization using randomly-permuted block sizes of four and six will be used to ensure balanced enrollment in each arm as the trial progresses. Randomization will also be stratified by anatomic region. The three anatomic regions include: head and neck (5 per arm), trunk and upper extremity (5 per arm), and lower extremity (10 per arm). Randomization sequences will be generated in advance using an available web service and the list will be maintained by a research nurse not involved in patient enrollment. (Sealed Envelope Ltd. 2015. Create a blocked randomization list. [Online] Available from: <https://www.sealedenvelope.com/simple-randomiser/v1/lists> [Accessed 12 Oct 2015].) Treatment allocation assignment for each patient will be kept in sealed envelopes by the research nurse until after the patient is enrolled in the study. As patients are being enrolled, the clinician enrolling the patient will contact this research nurse to obtain the treatment assignment and will not have a priori knowledge of the randomization of the patient. In order to ensure a manageable caseload, only 10 patients will be enrolled in the study at any one time. Once 10

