## Study Title: Prospective randomized clinical trial comparing outcomes of secondary intention wound care methods

healing time instead of a t-test. Time to healing in both groups will be plotted using Kaplan-Meier curves. The proportion of treatment failures in each group will be compared using chi-square or exact tests, as appropriate. Exploratory subgroup analysis for the above outcomes stratified by anatomic site, will be performed to assess for between-group differences across wound location. All tests will be two-sided with  $\alpha=0.05$ . Data will be analyzed using at Tufts CTSI using SAS or R software.

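### The primary analysis leaves out anatomic region, which randomisation is stratified by, and baseline wound size, so it gives up precision if these predict healing

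*Combined protocol and SAP*

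**What the plan says.** The randomisation section states: "Randomization will also be stratified by anatomic region". The regions are head and neck, trunk and upper extremity, and lower extremity, with 5, 5 and 10 patients per arm. Under Study Design / Procedures (Enrollment), wound width, length and depth are recorded at baseline before any intervention.

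In the Analytic Plan, between-arm differences in the primary outcome and the continuous secondary outcomes "will be analyzed using t-tests for independent groups". If healing time is not normal or any observation is censored, "a log-rank test will be used to test for differences in" healing time instead. No covariates or strata are named for either test. Region returns only as a secondary matter: "Exploratory subgroup analysis for the above outcomes stratified by anatomic site, will be performed". Baseline wound characteristics serve only as a check: "Differences in demographic and wound characteristics between groups will be compared to evaluate balance between groups". No adjusted model or adjusted sensitivity analysis is specified.

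The sample-size paragraph under Statistical Issues targets a 14-day difference and "assumed a standard deviation (SD) of 15 days". It does not say whether that SD is the total spread within an arm or the spread within a region.

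**The concern.** Stratified randomisation gives the two arms nearly the same mix of regions, so differences between regions hardly contribute to the treatment difference. A two-sample t-test does not know this and counts the between-region spread as noise. If region predicts healing time, the standard error is too large, the test falls below its stated alpha of 0.05, and the confidence interval that goes with it is too wide. Subgroup analyses by site estimate effects within regions and do not repair the main comparison.

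Wound size is a separate matter. It is not a stratification factor, so leaving it out does not make the standard error invalid. It only forgoes precision and leaves chance imbalance uncorrected.

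At stake is efficiency in a trial of 40 patients, whose own limitations paragraph already worries about variability greater than anticipated.

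**Working it through.** **The plan's own figure.** Inputs from Statistical Issues: difference 14 days, SD 15 days, 20 per arm, two-sided alpha 0.05. The standard error is 15 × √(2/20) = 4.74 and the noncentrality is 14/4.74 = 2.95. The noncentral t with 38 df gives 82.0% power; 19 per arm gives 79.9%. The stated 20 per arm is therefore correct for the stated test.

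**Assumptions for region.** The documents give no region means. Suppose leg wounds heal D days later than the other two regions, with D = 0, 7, 14 or 21. Half of each arm are leg wounds, so region adds variance D² × ½ × ½ = D²/4. The 15-day SD can be read in two ways:

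- Reading A, 15 is the total SD: within-region SD = √(225 − D²/4) = 15.0, 14.6, 13.3, 10.7. Region explains 0, 5, 22 and 49% of the variance.
- Reading B, 15 is the within-region SD: total SD = √(225 + D²/4) = 15.0, 15.4, 16.6, 18.3.

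For example, under A with D = 14 the region variance is 196/4 = 49 and the within-region SD is √176 = 13.3. The true standard error of the difference is 13.3 × √(2/20) = 4.2, but the t-test works with about 4.74.

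**t-test branch.** 100,000 simulated trials per scenario, exactly 5/5/10 per arm, normal errors. Each pair is unadjusted / adjusted for region.

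| Leg delay D (days) | A: power % | A: unadjusted type I error % | A: mean CI half-width (days) | B: power % | B: unadjusted type I error % | B: mean CI half-width (days) |
|---|---|---|---|---|---|---|
| 0 | 82 / 82 | 5.1 | 9.5 / 9.6 | 82 / 82 | 5.0 | 9.5 / 9.6 |
| 7 | 83 / 84 | 4.4 | 9.6 / 9.3 | 81 / 82 | 4.4 | 9.8 / 9.6 |
| 14 | 85 / 90 | 2.6 | 9.6 / 8.5 | 76 / 82 | 3.0 | 10.6 / 9.6 |
| 21 | 89 / 98 | 0.6 | 9.7 / 6.8 | 67 / 82 | 1.6 | 11.8 / 9.6 |

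The adjusted test stays at about 5% type I error. A separate set of 40,000 trials per scenario, set up by the share of variance that region explains, agrees. Under A at 20% it gives 84.7% against about 89.5% power, 2.8% unadjusted type I error and 97.2% unadjusted CI coverage.

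**Log-rank branch.** 20,000 trials per scenario, with an assumed control mean of 50 days outside the leg and censoring at day 112 (16 weeks; 1% or fewer censored). Power is unstratified / stratified by region.

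| Leg delay D (days) | A: power % | B: power % |
|---|---|---|
| 0 | 76 / 75 | 76 / 75 |
| 7 | 77 / 77 | 75 / 75 |
| 14 | 79 / 84 | 69 / 75 |
| 21 | 83 / 95 | 61 / 75 |

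The shortfall from 80% at D = 0 comes from changing tests, not from ignoring region, and under B stratifying does not restore 80%. The asymptotic stratified test has type I error of about 5.5% at this size. The unstratified test falls from about 6% at D = 0 to 1.4% (A) or 2.7% (B) at D = 21.

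**Wound size.** The documents do not say how much variance it explains. If covariates explain an assumed 20% or 40% of a 15-day total SD's variance, the residual SD is 15 × √0.8 = 13.4 or 15 × √0.6 = 11.6. With 35 residual df, power is then 89% or 96%, against 82% unadjusted.

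**The case against.** The strongest case on the other side is that nothing stated in the plan fails. An SD put into a two-group t-test is most naturally the total spread within an arm (Reading A), and there the unadjusted test keeps at least 82% power throughout. The drop below 80% appears only under Reading B. A clear gain under A needs a leg delay of 14 days or more, as large as the whole targeted effect; at 7 days the gain is one point. The unadjusted test is valid and conservative. All of this stands, and it limits the size of the point without removing it.

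The stratified log-rank also runs slightly above 5%: about 5.2 to 5.8% in the larger runs and 6 to 7% in a run of 1,500 trials. Held to a true 5%, its power under A is about 73, 75, 83 and 95%, so a little of the apparent gain is not real. The unstratified test is no better at zero offset, at about 6%, so this does not favour leaving region out.

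The wound-size part is the softest. Its explained variance is assumed, and nothing in the design obliges its inclusion. Fair too are the remarks that a linear model needs a rule for which values are judged for normality, and that number of complications is a count. These refine the fix but do not undo it.

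**Conclusion.** The concern holds. The plan stratifies by region and then analyses as if it had not, in both the t-test and the log-rank branch. The cost is lost efficiency, with no bias and no false-positive inflation, and it is conditional on region predicting healing.

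On the t-test branch, the power forgone at leg delays of 7, 14 and 21 days is about 1, 5 and 9 points if 15 days is a total SD, and about 1, 6 and 15 points if it is within-region. Only in the second case does power fall below the stated 80%, at the 14- and 21-day delays. The omission is certain from the text; the size of the loss is not, because the delays are assumptions. The figures also assume exact 5/5/10 allocation; simulating permuted blocks of four and six hardly changes them. This should be fixed, because the remedy is close to free.

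**What to change.** In the Analytic Plan:

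- Replace the primary t-test with a linear model of days to healing on arm, region (three levels) and log baseline wound area (length × width). Report the adjusted difference with its 95% CI. With 40 patients, keep to these terms.
- Say that the normality condition is judged on the model residuals.
- On the fallback branch, use a log-rank test stratified by region, with a region-stratified Cox model including log baseline area for the effect estimate. Acknowledge that the asymptotic test runs slightly above 5% at this size; a permutation version within region would deal with that.
- Apply the same region adjustment to the continuous secondary outcomes, noting that number of complications is a count.
- Keep the baseline comparison for description only.

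In the Enrollment paragraph, state that the wound is measured before the allocation is revealed. As written, baseline-visit data are obtained "after the patient has signed consent and been randomized to their specific treatment arm". No biased measurement is shown, but a covariate is better fixed beforehand. In the sample-size paragraph, say whether the 15-day SD is total or within-region.

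The cost is SAP wording, a few lines of code and the order of two steps at one visit. If region has no effect, the adjusted t-test branch loses nothing measurable (82% against 82%) and the stratified log-rank loses about 1 to 2 points (76% against 75%). The changes should be made before any analysis by arm, while the model can still be prespecified.
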